## Study Protocol

### Objectives and Hypotheses:

The *HealthMatters @ 24/7 eLearning* project has three objectives:

**Objective:** Test the effectiveness of an on demand e-Learning platform (HealthMatters@24-7) for staff in CBOs in one state.

HO1. **More CBOs** in the asynchronous training program will have developed Strategic Action Plans for Health and Wellness, established Wellness Committees, and have equal or more resources and improved culture for health promotion at 3 months compared to CBOS participating in the current live *HealthMatters TtT Workshop* webinar.

HO2. **Staff** in the asynchronous training group will have improved level of learner/instructor satisfaction toward the training immediately after completing the enhanced mode of training, *HM@24/7* compared to staff trained using the current live *HealthMatters TtT Workshop* webinar.

**Design.** We will utilize two groups (Table 1), random selection, pre-test/post test experimental design where Experimental Group receives *HealthMatters@24/7* training and Control Group receives the usual real-time (live) webinar training (*HealthMatters Train the Trainer Workshop*).

**Measures. HO1, HO2, and HO4 Measures.** *Process Evaluation* (assessment of changes in policy and fiscal strategic plans). Throughout the program, process evaluation will be used to continuously provide data for program improvement efforts and communicate new information through as many channels as possible to reach target audience. Process evaluation questions are in **Appendix B. HO3 Measures** will be collected using an online organizational HealthMatters Assessments (oHMA) via Qualtrics. oHMA evaluates organizational **needs** and **capacity** for developing a health promotion plan including programs, services, environmental support, resources, culture, and employee knowledge and skills to do health promoting activities. Please see **Table 2** for reliability and validity information. Data will be collected from CBO staff before at baseline and at 1 year. Staff outcome expectations, barriers to exercise and nutrition, self-efficacy for health promotion and health promotion knowledge, and health advocacy will also be assessed via online HMAs. The data will be collected before HMP at baseline, 3, 12, and 24 months after implementation of the *HMP* intervention.

**Table 2. Reliability and Validity of HealthMatters Assessments**

Organizational Capacity Checklist	Reliability coefficients for the Organizational Capacity Checklist subscales (e.g., organization commitment, supportive health promotion policies, policies supporting staff to do health promotion, and organizational resources) ranged from .92 - .81. Test/retest correlations ranged from .83 - .74.
Employee Capacity Checklist	Reliability coefficients for the Employee Capacity Checklist subscales (e.g., confidence doing health promotion, agency policies, agency resources, and health promotion knowledge) ranged from a= .90 - .67. Test/retest ranged from .74 - .58.
Exercise and Nutrition Outcome Expectations (OE); Barriers to Exercising and Nutrition	OE: Exercise: a=.81; test/retest =.60; Nutrition: a=.81; test/retest =.59 Barriers: Exercise: a= .88; test/retest = .54; Nutrition: a= .80; test/retest = .57
Self-Efficacy for Teaching Exercise Activities	(a= .94; test/retest = .68)

## Statistical Analysis Plan

**Data Analysis.** With a minimum of 20 CBOs, 60 employees (30 in each group) and 160 individuals with IDD (80 in each group) participating in the *12-week HealthMatters Program*, the proposed project will have a 95% power to detect a small effect size of 0.08 between the *HealthMatters@24/7* intervention and the *HealthMatters Live* webinar control groups using a 2-sided alpha 0.05 and an estimated intraclass correlation (ICC) of 0.5. While the actual effect size

is unknown due to its novel nature, the proposed sample size should be adequate to detect a minimum meaningful difference in study outcomes between the two experimental groups as we anticipate a small to moderate effect size resulting from the *HealthMatters @ 24/7 e-Learning*.

Data were electronically collected throughout the project. Descriptive statistics will be obtained for all study variables. Tests of significance will be based on an alpha level of .05. Repeated measures analysis of variance (RM-ANOVA) will be employed to examine whether outcome measures of self-efficacy, barriers, outcome expectations, and health advocacy for DSP will be more favorable for the *HealthMatters asynchronous group* compared to *synchronous group*. Multi-level hierarchical liner modeling (HLM) analysis will be done to estimate separately the variance between DSPs within the same CBO, and the variance between CBOs. We will examine group-level and individual-level factors with multilevel analysis to allow for variance in outcome variables that can be analyzed at multiple hierarchical levels.

**Informed Consent Form.** No informed consent form was needed. Per “Study IRB Protocol #2020-0754 Exempt Research” was determined under **exemption category under 45 CFR 46.101(b) in that** information obtained was recorded in such a manner that no human subjects could be identified, directly or through identifiers linked to the study participants.

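### The SAP names RM-ANOVA for the staff outcomes without a baseline covariate, a chosen F test or stated waves; against baseline adjustment this costs from about 10% of power to more than half

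*Combined protocol and SAP*

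**What the plan says.** The Data Analysis paragraph of the SAP states that "Repeated measures analysis of variance (RM-ANOVA) will be employed to examine whether outcome measures of self-efficacy, barriers, outcome expectations, and health advocacy" for direct support staff are better in the asynchronous group. It does not say whether the test is the group main effect or group by time, which waves enter, or how the baseline score is used. Hierarchical linear modelling is named next, to separate variance within and between CBOs and to examine unspecified factors at group and individual level. Neither arm nor baseline score is named as a term in it.

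On timing, the Measures paragraph of the protocol says of the staff scales: "The data will be collected before HMP at baseline, 3, 12, and 24 months after implementation". Table 1, by contrast, shows one pre-test and one post-test.

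Table 2 gives test/retest values for three of the four constructs, the lowest being "Barriers: Exercise: a= .88; test/retest = .54" and the highest .68 for self-efficacy. It has no entry for health advocacy.

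The sample size paragraph gives "With a minimum of 20 CBOs, 60 employees (30 in each group) and 160 individuals with IDD (80 in each group"), with tests "using a 2-sided alpha 0.05 and an estimated intraclass correlation (ICC) of 0.5". On the size of effect it says "as we anticipate a small to moderate effect size".

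**The concern.** If arms are randomly assigned, their expected baselines are equal, and the baseline score is best used to explain variation in the follow-up scores. RM-ANOVA in its usual form makes baseline a level of time instead.

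- **Group main effect.** It averages in a wave that carries no treatment effect.
- **Four-wave group-by-time F.** It spreads the question over 3 df and has no direction, although the SAP asks whether one group does better.
- **Pre/post group-by-time F.** It is a change-score test, which subtracts too much of the baseline when the correlation is well below 1.

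With about 10 CBOs per group, precision is scarce, and the baseline survey is already scheduled. The silence on which F test applies also leaves a choice, open after the data are seen, among tests whose power differs widely. At stake is the chance of detecting a real difference on the staff scales. The loss would occur with complete data and with correct handling of clustering.

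**Working it through.** **The plan's own power figure.** The SAP claims "95% power to detect a small effect size of 0.08" without naming the metric. Read as a standardised mean difference with 30 staff per arm, power is about 0.06, and 95% would need 2 × (1.960 + 1.645)² / 0.08² ≈ 4,061 per arm before clustering. The nearest match found is f² = 0.08 with 160 people and no clustering (0.945), which is not the staff sample and drops the stated ICC. The figure is therefore no benchmark here, and I compare tests at assumed effects instead.

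**Inputs from the documents.** 30 staff per arm in 20 CBOs (about 3 per CBO); "an estimated intraclass correlation (ICC) of 0.5"; two-sided alpha 0.05; baseline plus k = 3 later waves (Measures) or k = 1 (Table 1); r = .54, .60, .68 (Table 2).

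**Assumptions.** d = 0.2, 0.35 and 0.5 for small to moderate, with 0.8 as sensitivity; equal correlation r between all waves and at both levels; constant effect after baseline; no dropout; random assignment of CBOs.

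**Clustering.** Design effect 1 + (3 − 1) × 0.5 = 2, so n = 15 effective per arm. CBO-level error df are 18 for the between-group tests and 17 after one baseline covariate.

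**Formulas.** With T = k + 1, the noncentrality is (n/2) × d² times:
- group main effect: (k/T)² / [(1 + (T − 1)r)/T]
- group by time: (k/T)/(1 − r), on k df as the omnibus test or 1 df as the post-mean-minus-baseline contrast
- baseline-adjusted post mean: 1 / [(1 + (k − 1)r)/k − r²], on 1 df

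**Worked case, d = 0.5, r = .60, design effect 2.** (n/2)d² = 7.5 × 0.25 = 1.875.

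| Test | Multiplier | Noncentrality | Power |
|---|---|---|---|
| Four waves: group main effect | 0.5625/0.70 = 0.804 | 1.51 | 0.21 |
| Four waves: group by time, 3 df | 0.75/0.40 = 1.875 | 3.52 | 0.30 |
| Four waves: change contrast, 1 df | 1.875 | 3.52 | 0.43 |
| Four waves: baseline-adjusted post mean | 1/0.3733 = 2.679 | 5.02 | 0.56 |
| Pre/post: group by time | 0.50/0.40 = 1.25 | 2.34 | 0.30 |
| Pre/post: baseline-adjusted | 1/0.64 = 1.563 | 2.93 | 0.37 |

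**Share of baseline-adjusted power kept, r = .54 to .68, d = 0.2 to 0.5.**

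| Test | No clustering | Design effect 2 |
|---|---|---|
| Pre/post group by time | 81–90% | 81–91% |
| Four-wave group by time, 3 df | 48–75% | 49–62% |
| Four-wave group main effect | 32–50% | 32–60% |

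The 60% at the top of the last row occurs at d = 0.2, where no test exceeds 15% power. At d = 0.35 to 0.5 with clustering, the main effect keeps 32–45%.

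**In information terms.** The change/baseline-adjusted ratio is (1 + r)/2 = .77 to .84 for one post wave. For the 1-df contrast with three post waves it is .66 to .76.

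**Larger effects.** At d = 0.8, the 3-df interaction keeps 67–82% with design effect 2 and 92–99% without clustering.

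**Effect not constant (d = 0.5, r = .60, no clustering).**

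| Effect pattern | Group by time, 3 df | Adjusted post mean | Adjusted 3 months |
|---|---|---|---|
| Constant | 0.58 | 0.88 | 0.66 |
| 3 months only | 0.58 | 0.18 | 0.66 |
| Rising (1/3, 2/3, 1) | 0.45 | 0.55 | 0.125 |

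**The case against.** The strongest reply is that the SAP nowhere says that baseline enters as an outcome wave. A reader might infer this from the name RM-ANOVA and the four-wave schedule, and conclude that about half the power is lost. The documents do not support that as fact: Table 1 fits a pre/post group-by-time test, for which the loss is only about 10–20%. This objection stands, and the loss must be given as a range by test.

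A reader might also take RM-ANOVA to be the only between-group method in the plan. That is too strong. The hierarchical model is named too, and arm and baseline could be among its factors. But neither is specified, so the model does not supply the missing adjustment.

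Three further points stand as limits:

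- **Assignment.** The documents describe an experimental design with random selection and say CBOs enrolled in one group or the other; random assignment is implied but not described. If arms differed at baseline by a stable amount D with no treatment effect, change scores would be unbiased, while baseline adjustment would be biased by about D(1 − r), or .32D to .46D.
- **Correlation.** Test/retest values are proxies for correlations over 3 to 24 months. CBO means may correlate more strongly: at r = .80 the information ratios rise to .90 (one post wave) and .85 (three), and the gain over change scores shrinks.
- **Contrast.** The adjusted post mean is not uniformly better. It loses to the 3-df interaction if the effect is confined to 3 months.

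**Conclusion.** The concern holds as a gap in specification with a range of cost. The SAP ties only RM-ANOVA to the staff group comparison and leaves the F test, the waves and the baseline handling open. In every constant-effect scenario run, the baseline-adjusted analysis had more power than the corresponding RM-ANOVA test. At small-to-moderate effects the relative loss is about 10–20% (pre/post group by time), roughly 25–50% (four-wave 3-df interaction), or about half or more (four-wave group main effect; nearer 40% only at d = 0.2 with clustering). These sizes rest on random assignment of CBOs, a constant post-baseline effect, complete data, and Table 2 values as proxies, with none available for health advocacy.

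A reader might infer that the trial is more likely to miss its main result. The documents do not support that. HO1 concerns CBO plans, committees, resources and culture, and HO2 concerns satisfaction right after training. The four staff scales are in neither. The loss is one of precision on staff outcomes.

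**What to change.** Replace the RM-ANOVA sentence. For each staff scale, specify a mixed model with the post-baseline waves as outcome, the person's baseline score and the CBO mean baseline as covariates, CBO and person as random effects, and arm as a fixed effect. Name one 1-df arm contrast as the test.

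Choose that contrast in advance: the 3-month difference or the average over post-baseline waves. Averaging loses power if the effect is confined to 3 months, and the 3-month contrast loses power if the effect builds up later. The choice should follow from when the effect is expected. Reconcile Table 1 with the Measures paragraph on the number of post waves.

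State that CBOs were randomly assigned. If they were not, report the change-score contrast as a sensitivity analysis.

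The cost is SAP wording and one or two degrees of freedom for the covariates. No new data are needed: the model requires each person's waves to be linked, as RM-ANOVA already does.
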